6.7 BASELINE, TIME WINDOWS AND CALCULATED VISITS

In general, baseline values are the measurements taken prior to the first administration of trial medication. For assessments of efficacy, PANSS and C-SSRS, baseline will be defined as the last available assessment performed at or before randomization (Visit 2), and no later than the day of the first administration of study medication. Assessments done at Visit 1 or Visit 1a can be used as baseline if Visit 2 assessment is not planned, not available, or invalid.

For MCCB, only the assessment performed at randomization (Visit 2), and no later than the day of the first administration of study medication will be used as the baseline. If no valid assessment is available at Visit 2 then baseline value will be missing; assessments performed at Visits 1 and 1a will not be used as baseline.

Tables in this section define the analysis visits and windows which will be used for the analyses of efficacy and safety endpoints. Actual study day will be calculated starting with the date of first administration of trial treatment as Day 1. Unscheduled assessments will be mapped to the analysis visits together with the scheduled assessments.

Inclusion of an assessment into mapping consideration will depend on its on-/off-treatment status and per specific estimand (i.e., off-treatment data will be included into mapping consideration only when the associated ICE is handled under the treatment policy approach). If more than one assessment falls into the same analysis visit window, the assessment performed closest to the planned day will be selected for analyses. In case of a tie, the later assessment will be used.

Table 6.7: 1 Analysis visit windows for MCCB, VRFCAT, SCoRS, and PANSS

Analysis Visit	Nominal Week	Planned Day	Actual Day Window
Baseline		1	≤ 1
Visit 6	Week 12	85	2 – 126
Visit 11	Week 26	183	≥ 127

Table 6.7: 2 Analysis visit windows for PRECIS, EQ-5D-5L (patient)

Analysis Visit	Nominal Week	Planned Day	Actual Day Window
Baseline		1	≤ 1
Visit 7	Week 15	106	2 – 126
Visit 10	Week 24	169	≥ 127

Table 6.7: 3 Analysis visit windows for Tower of London, SDS, EQ-5D-5L (caregiver), SPGI-S, SCQ

Analysis Visit	Nominal Week	Planned Day	Actual Day Window
Baseline		1	≤ 1
Visit 10 (for SDS only)	Week 24	169	≥ 2
Visit 11 (for Tower of London, EQ-5D-5L (caregiver), SPGI-S, and SCQ)	Week 26	183	≥ 2

Table 6.7: 4 Analysis visit windows for CGI-S

Analysis Visit	Nominal Week	Planned Day	Actual Day Window
Baseline		1	≤ 1
Visit 6	Week 12	85	2 – 126
Visit 10	Week 24	169	127 – 175
Visit 11	Week 26	183	≥ 176

Table 6.7: 5 Analysis visit windows for PGI-S

Analysis Visit	Nominal Week	Planned Day	Actual Day Window
Baseline		1	≤ 1
Visit 10	Week 24	169	2 – 175
Visit 11	Week 26	183	≥ 176

Table 6.7: 6 Analysis visit windows for SAS/BARS/AIMS

Analysis Visit	Nominal Week	Planned Day	Actual Day Window
Baseline		1	≤ 1
Visit 4	Week 6	43	2 – 74
Visit 7	Week 15	106	75 – 137
Visit 10	Week 24	169	138 – 175
Visit 11	Week 26	183	≥ 176

Table 6.7: 7 Analysis visit windows for clinical laboratory evaluations (on-treatment period)

Analysis Visit	Nominal Week	Planned Day	Actual Day Window
Baseline		1	≤ 1
Visit 2	Week 0 (post-baseline)	1	2 – 35
Visit 4	Week 6	43	36 – 77
Visit 6	Week 12	85	78 – 119
Visit 8	Week 18	127	120 – 140
Visit 9	Week 21	148	141 – 161
Visit 10	Week 24	169	162 – 175
Visit 11	Week 26	183	≥ 176

All post-baseline actual day windows will be curtained at the end of residual period if earlier than the specified upper bound in the table.

Table 6.7: 8 Analysis visit windows for weight and vital signs (on-treatment period)

Analysis Visit	Nominal Week	Planned Day	Actual Day Window
Baseline		1	≤ 1
Visit 2	Week 0 (post-baseline)	1	2 – 56
Visit 5	Week 9	64	57 – 119
Visit 8	Week 18	127	120 – 175
Visit 11	Week 26	183	≥ 176

All post-baseline actual day windows will be curtained at the end of residual period if earlier than the specified upper bound in the table.

Table 6.7: 9 Analysis visit windows for Ophthalmological variables

Analysis Visit	Nominal Week	Planned Day	Actual Day Window
Baseline		-7	≤ 1
Visit 10	Week 24	169	≥ 2

Note that for placebo patients who rolled over to the extension study, any ophthalmological assessments incidentally performed after the first administration of icleperitin in the extension study will not be included in the safety analysis.

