### **3.3.3 Exclusion criteria**

1. Participant with current DSM-5 diagnosis other than Schizophrenia, including but not limited to bipolar, schizoaffective, major depressive disorder etc. M.I.N.I. for Psychotic disorders should be used for guidance.
2. Cognitive impairment due to developmental, neurological (e.g., stroke) or other disorders including head trauma, patients with dementia or epilepsy.
3. Severe movement disorders
  - Leading to cognitive impairment (e.g. Parkinson dementia), or
  - Interfering with the efficacy assessments, or
  - Due to antipsychotic treatment that cannot be controlled with low dose anticholinergic treatment (equal to maximum 1 mg benzotropine twice daily). Table of relevant medications and their equivalencies will be provided as a part of ISF
4. Any suicidal behavior in the past 1-year prior to screening and during the screening period.
5. Suicidal ideation of type 5 in the C-SSRS (i.e. active suicidal thought with plan and intent) in the past 3 months prior to screening and up to and including Visit 2.
  - Patients with Suicidal Ideation type 4 in the C-SSRS (i.e. active suicidal thought with intent but without specific plan), within 3 months prior to screening and up to and including Visit 2, can be randomized in the study, if assessed and documented by a licensed mental health professional that there is no immediate risk of suicide.
6. History of moderate or severe substance use disorder (other than caffeine and nicotine), as defined in DSM-5 within the last 12 months prior to informed consent.
7. Positive urine drug screen at Visit 1 based on central lab test. For a list of drugs assessed in the urine drug screen, please refer to [Table 5.2.3:1](#).
8. Patients who were treated with any of the following within 6 months prior to randomization:
  - Clozapine
  - Stimulants (e.g. methylphenidate, dextroamphetamine, modafinil)
  - Ketamine or esketamine
  - Electroconvulsive therapy (ECT) or Modified ECT
9. Participation in any investigational psychoactive drug trial (both industry/ academic) in last 6 months, and 30 days or 5 half-lives for no-psychoactive drug trial, prior to randomization.
10. Patients who were previously treated with Iclepertin.

Proprietary confidential information © 2024 Boehringer Ingelheim International GmbH or one or more of its affiliated companies

11. Patients who are treated with any of the following within the last 35 days prior to randomization:

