The C-SSRS is a semi-structured, investigator-rated interview, developed by clinical experts in cooperation with the FDA, assessing both suicidal behavior and suicidal ideation. It does not give a global score but provides some categorical and some severity information specifically for behavior and ideation.

The computer-automated C-SSRS interview may be administered using a tablet device.

Subjects who do not have suicidal behavior or ideation will answer a limited number of questions and will usually complete the assessment in about 3 minutes. Subjects with significant suicidal ideation or behavior may require up to 10 minutes to answer all relevant questions. This assessment should be conducted early in the visit. At the conclusion of each assessment, the site will have access to the C-SSRS results. The results include the findings for suicidal ideation, intensity of ideation, suicidal behavior, and lethality / medical damage (for actual suicide attempts only).

The C-SSRS has been widely used in large multinational clinical trials. The C-SSRS will be administered first at screening (Visit 1) (using the 'Baseline / Screening' version) with the aim to exclude subjects with active moderate or severe symptomatology within a specified time prior to screening. The lifetime history of suicidal ideation and behavior will also be recorded.

After screening (Visit 1) the assessment 'since last visit' will be performed at each clinic visit ('Since Last Visit version'). The investigator is to review/ consider the C-SSRS results for plausibility and clinical relevance. Doubtful results may be repeated or results may be validated by a consulting psychiatrist. If there is a confirmed positive report of suicidal behavior or suicidal ideation type 4 or 5 after start of trial, the investigator is to immediately interview the subject during the clinic visit (if the investigator did not administer the C-SSRS leading to the positive report), and/ or is to consult a psychiatrist if considered necessary.

For any positive suicidal ideation (type 1 to 5) or suicidal behavior, the rater must document additional details in the comment fields in the C-SSRS in Pathway.

If there is any new suicidality or increase in suicidality, please comment on the clinical significance and any additional follow-up actions that may be performed in the eCRF.

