#### 6.2.3.1 Randomization (Visit 2)

- It should be ensured that all Visit 1 and Visit 1a procedures have been successfully completed.
- MCCB is to be done before any other efficacy assessments.
- Study procedures for Visit 2 can be split into 2 sequential days, in which case:
  - The MCCB and VRFCAT must be performed on the first day.
  - The remaining assessments can be done per the convenience of the patient and site, either on day 1/ day 2.
  - To reduce burden on study partner, it is recommended to perform PANSS and SCoRS on the same day.
  - In case of a split visit, the second day will be day of first study drug intake.

Proprietary confidential information © 2024 Boehringer Ingelheim International GmbH or one or more of its affiliated companies

- Biobanking sample, for patients who have signed the optional Biobanking consent form, should be collected before the intake of the first dose of study medication (refer to [Section 5.5.1](#)).
- **The MCCB overall T-score from the visit 1 (screening) is required for randomization at visit 2.**
  - In case that screening MCCB T-score is not available at visit 2, site may postpone this visit by maximum of 2 weeks.
- Patient eligibility must be confirmed before the patient is randomized in the IRT. Intake of the study medication must be done after the patient has completed all of the other visit 2 assessments.
- First intake of trial drug will be done on site using the [REDACTED] medication adherence monitoring app and under supervision by trial staff.
- The first two medication kits will be dispensed and will contain sufficient trial drug for 28 days (21 treatment days plus 7 days reserve). For further information refer to [Section 4.1.4](#).
- At each clinic visit, patients should be reminded not to take study medication AT HOME on the morning of the visit. At each visit, patient will take medication AT THE CLINIC using [REDACTED] under supervision by trial staff.

#### 6.2.3.2 Visit 3 to Visit 10

- Pre-dose PK blood samples will be collected during the treatment period as per the [Flow Chart](#). Patients should not take trial medication before coming to the clinic on visit days. Refer to [Section 5.3](#) and [Appendix 10.1](#) for more details.
- Patients should be instructed to bring all trial medication (used and unused kits/ packaging including blisters) with them to these clinic visits.

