4. CHANGES IN THE PLANNED ANALYSIS OF THE STUDY

For the further endpoint of change from screening Visit 1a in PRECIS individual items and domain scores at Week 24, only the PRECIS domain scores will be analyzed, and the PRECIS individual items will not be analyzed.

Definition of baseline for the assessments of efficacy, PANSS and C-SSRS will include assessments up to but no later than the day of the first administration of study medication.

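### The SAP's last-assessment rule gives the C-SSRS a baseline that recalls about 7 to 14 days, so recurrence of recorded ideation can be classed as new on treatment

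*SAP*

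**What the plan says.** **The baseline rule.** SAP 6.7 states: "For assessments of efficacy, PANSS and C-SSRS, baseline will be defined as the last available assessment performed at or before randomization (Visit 2". It adds: "Assessments done at Visit 1 or Visit 1a can be used as baseline if Visit 2 assessment is not planned, not available, or invalid". SAP Section 4 lists the definition among the changes to the planned analysis: "Definition of baseline for the assessments of efficacy, PANSS and C-SSRS will include assessments up to but no later than the day" of first dosing. The MCCB gets its own exception in SAP 6.7; the C-SSRS does not.

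**The instrument.** Protocol 5.2 gives the screening version at Visit 1: "The lifetime history of suicidal ideation and behavior will also be recorded". After Visit 1 the since-last-visit version "will be performed at each clinic visit". The Flow Chart schedules the C-SSRS at Visits 1, 1a and 2 and at every later visit.

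**Who can enter.** Protocol 3.3.3 excludes suicidal behaviour in the year before screening and during screening, and type 5 ideation from 3 months before screening through Visit 2. Patients with type 4 ideation "within 3 months prior to screening and up to and including Visit 2, can be randomized in the study" if a licensed mental health professional documents no immediate risk. No criterion addresses types 1 to 3.

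**The analysis.** Suicidality by C-SSRS is a further safety endpoint (Protocol 2.2.2.2). Protocol 7.2.5 plans descriptive summaries without hypothesis tests.

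**The concern.** A last-value baseline suits a scale that measures current state, such as the PANSS. The C-SSRS instead records whether something happened during a recall interval, so its baseline is only as informative as that interval is long. Under SAP 6.7 the longest pre-treatment record, from Visit 1, is set aside whenever a later form exists.

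The protocol describes suicidal ideation and behaviour as common in this population, and it knowingly admits some patients with recent ideation. In such a patient, two quiet weeks before Visit 2 give a baseline of no ideation, and the next episode then looks like onset on drug or placebo. At stake is how specific the new or worsened category is for a listed safety endpoint.

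The meaning of baseline also varies between patients. It is a short interval for most, but the history-bearing screening version for anyone whose Visit 1a and Visit 2 forms are both missing or invalid.

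**Working it through.** The documents give no figure to reproduce. The check derives the recall intervals and then asks how much they could matter.

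**Recall intervals, from the Flow Chart windows**
- Visit 1 is on Day -35 to -28 and Visit 1a on Day -14 to -7. The Visit 2 form therefore looks back 7 to 14 days.
- Protocol 6.2.3.1 allows a delay if the screening MCCB score is late: "site may postpone this visit by maximum of 2 weeks". If Visit 1a has already taken place, recall is 7 + 14 = 21 to 14 + 14 = 28 days.
- If Visit 1a is the fallback baseline, recall is 28 - 14 = 14 to 35 - 7 = 28 days.
- On treatment, visits are nominally 21 days apart, with 14 days from Visit 10 to end of treatment. The whole span is 183 - 1 = 182 days.

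**Recall mismatch, on schedule**
- By-visit display: 14/14 = 1 to 21/7 = 3 fold.
- Any-time-on-treatment display: 182/14 = 13 to 182/7 = 26 fold.
- With a postponed Visit 2, the any-time ratio falls to 182/28 = 6.5 to 182/21 = 8.7 fold.

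**What recall length alone does.** Assume a constant rate, no drug effect, and a proportion p of patients with any ideation in 26 weeks. The rates are assumptions; the documents give none. P(positive in d days) = 1 - (1 - p)^(d/182).

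| Recall | p = 10% | p = 20% |
|---|---|---|
| Visit 2 form, 7 to 14 days | 0.4 to 0.8% | 0.9 to 1.7% |
| One on-treatment form, 21 days | 1.2% | 2.5% |
| 3-month look-back, 90 days | 5.1% | 10.4% |
| Any time on treatment, 182 days | 10% | 20% |

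**What a longer baseline would change.** Suppose a patient has episodes at random with a mean interval of T days, unchanged by treatment. With baseline look-back L, P(classed as new) = exp(-L/T) × (1 - exp(-182/T)). Compare L = 7 to 14 days (the SAP rule) with L = 91 + 28 = 119 to 91 + 35 = 126 days (3 months before Visit 1 plus screening).

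| Mean interval T | SAP rule | Pooled Visits 1, 1a and 2 |
|---|---|---|
| 30 days | 63 to 79% | about 2% |
| 91 days | 74 to 80% | 22 to 23% |
| 182 days | 58 to 61% | 32 to 33% |
| 365 days | 38 to 39% | about 28% |

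The gain is largest for patients with frequent recurrence, which is the group the rule misclassifies. It is small when episodes are rare and spread evenly. At p = 10% in every patient, the share classed as new is 10% × 0.9^(L/182), which is 9.9 to 10.0% under the SAP rule and 9.3% with the pooled baseline. The effect on the overall count therefore depends on how far ideation clusters in the same patients, which the documents do not report.

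**The case against.** **The tabulation cannot be seen.** No visible text defines new or emergent C-SSRS findings, and SAP 6.7 gives no visit-window table for this scale. Parts of the SAP are redacted and may show prior history beside baseline. This stands. A reader might infer that suicidality will be reported as emergent; the documents support only that it can be.

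**The large ratio is one case.** On-treatment forms are also since-last-visit forms, so a by-visit table compares similar intervals. This stands. The 13 to 26 fold figure applies only to a display of any finding on treatment.

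**The cases can be told apart.** A reader might infer that patients with prior ideation are lost among true new cases. They are not: Visit 1 records the history, raters must document details of any positive report, and the investigator comments on new or increased suicidality. The fault is in the baseline variable and not in the data collected.

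**Safety reporting does not depend on it.** Protocol 5.2.6.1.4 makes behaviour and type 4 or 5 ideation SAEs, and types 1 to 3 SAEs when judged an AE. None of this uses the C-SSRS baseline.

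**Exposure is limited.** Behaviour in the past year and recent type 5 ideation are excluded, so the recent findings at issue are ideation of types 1 to 4. Because Visit 2 assessments must be completed before dosing, fallback to the Visit 1 form should be uncommon.

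These points reduce the consequence. They do not alter the fact that SAP 6.7 names the C-SSRS and gives it a baseline with short recall.

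**Conclusion.** The point holds as a fault in a stated definition. On schedule the C-SSRS baseline recalls 7 to 14 days, and up to about 28 days if Visit 2 is postponed. Ideation recorded at Visit 1 is dropped whenever a valid later form exists. Any comparison with this baseline can class recurrence as new or worsened, with a scheduled recall mismatch of roughly 1 to 3 fold by visit or 13 to 26 fold over the whole treatment period.

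The recall intervals come from the Flow Chart. The percentages rest on assumed event rates and a constant-rate model, and serve only as illustration.

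A reader might also infer a bias for or against iclepertin. The documents do not support that: the same rule applies to both randomised arms, so the artefact should be similar in each. It adds non-specific cases to both, which makes a real difference harder to read.

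**What to change.** In SAP 6.7, and to match in Section 4, remove the C-SSRS from the last-available-assessment rule. Define its baseline as the most severe ideation type and any behaviour across Visit 1 (using the protocol's own look-backs of 3 months for ideation and 1 year for behaviour), Visit 1a and Visit 2. Count on-treatment findings as new or worsened against that value, and show lifetime history separately.

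The cost is one SAP sentence and minor programming. All the data are already collected, and no visit, assessment or eligibility rule changes. Counts of emergent cases will be somewhat lower and more specific. If a redacted section already shows pre-treatment history beside the C-SSRS results, a cross-reference from SAP 6.7 would help, but the baseline definition should still be corrected.

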6. GENERAL ANALYSIS DEFINITIONS

6.1 TREATMENT(S)

For basic study information on treatments to be administered, assignment of treatment groups, select of doses, see CTP Section 4.

Table 6.1: 1 lists the two treatment groups in this study. Table 6.1: 2 defines the analysing treatment period for safety analyses. For this study, the residual effect period (REP) is defined as 12 days after the last dose of trial medication.

Table 6.1: 1 Treatment descriptions

Long Name	Short Name
Placebo	Placebo
Iclepertin 10 mg QD	Iclepertin 10 mg

Table 6.1: 2 Analysing treatment periods (same for all treatment groups)

Analysing Treatment Period	Start Date	End Date
Screening period	Date of informed consent	Date of the first treatment administration – 1 day
On-treatment period	Date of the first treatment administration	Date of the last treatment administration + REP
Post-treatment period	Date of the last treatment administration + REP + 1 day	Date of the last per protocol visit

REP is the residual effect period which is defined as 12 days after the last dose of trial treatment.

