6.3 INTERCURRENT EVENTS

Definition and technical specification of protocol defined intercurrent events (ICEs) are listed in [Table 6.3: 1](#). In general, when handled under the hypothetical approach, data collected during the off-treatment period of an ICE will be considered irrelevant to the estimand and excluded from the analysis. While off-treatment data will be excluded, the patient will still be considered as on-treatment (hypothetically) from an analysis perspective by the statistical models, and during any imputations.

For an ICE of temporary treatment discontinuation or interruptions, the off-treatment period spans from the last treatment administration prior to the interruption + REP to the restart of

the study medication. For an ICE of early permanent treatment discontinuation, the off-treatment period starts from the last treatment administration + REP. [Figure 6.3: 1](#) illustrates the on-/off-treatment status after each type of ICEs. When there is more than one ICE of early permanent treatment discontinuation, any treatment policy ICE take precedence in data and analysis handling over any hypothetical ICE.

ICEs of change in concomitant therapies and other ICEs will always be considered as part of the treatment policy in the primary and all supplementary estimands. ICEs of this category will not affect the on-/off-treatment status which is only determined by changes in the study medication. These ICEs will be listed and summarized descriptively but will not be explicitly accounted for in the inferential analysis of efficacy.

Table 6.3: 1 Definition and technical specification of intercurrent events

Type of Intercurrent Event	Definition and Documentary Sources	Handling under the Primary Estimand
Temporary Treatment Discontinuations or Interruptions		
Exacerbation or acute episode of schizophrenia resulting in interruption of treatment	
Identified from data collected in the Temporary Trial Treatment Discontinuation and Adverse Event pages of the CRF:
 
 - Temporary discontinuation of trial treatment reported with reason being “Adverse Event”, and - AE category reported as “Schizophrenia Relapse” or MedDRA preferred term coded as “Schizophrenia” 	Treatment policy

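### Early end-of-treatment Tower of London scores can enter the Week 26 ANCOVA for H4 as if measured at Week 26

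*SAP*

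**What the plan says.** - **Window.** SAP 6.7, Table 6.7: 3 has one post-baseline row for this scale: "Visit 11 (for Tower of London, EQ-5D-5L (caregiver), SPGI-S, and SCQ"), Week 26, planned Day 183, actual day 2 or later.
- **Eligibility.** SAP 6.7 states that "off-treatment data will be included into mapping consideration only when the associated ICE is handled under the treatment policy approach". On-treatment data are always eligible.
- **On-treatment status.** In SAP 6.1 "the residual effect period (REP) is defined as 12 days after the last dose of trial medication". SAP 6.3 adds: "For an ICE of early permanent treatment discontinuation, the off-treatment period starts from the last treatment administration + REP".
- **Choice within a window.** If several tests qualify, "the assessment performed closest to the planned day will be selected for analyses".
- **Schedule.** The Protocol Flow Chart places Tower of London, after baseline, only at EOT/Visit 11 and at eEoT. Protocol 6.2.5.1 asks for the eEoT visit preferably within 7 days of the last dose.
- **Model.** SAP 7.5.2 applies the primary intercurrent-event strategy to this endpoint and fits an ANCOVA with treatment, stratum and baseline. There is no visit term.
- **Other tested endpoints.** The tables titled "Analysis visit windows for MCCB, VRFCAT, SCoRS, and PANSS" and "Analysis visit windows for PRECIS, EQ-5D-5L (patient") start the final window at Day 127 and send Days 2-126 to an earlier visit.

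**The concern.** H4 is an alpha-controlled hypothesis in Family 3, defined as change from baseline to Week 26. Under the visible mapping rule, some of the values labelled Week 26 were measured when the patient stopped treatment, possibly months earlier. If benefit builds over time, the reported difference is a mixture over stopping times and is diluted against the true Week 26 effect.

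Protocol 2.1.1 describes the effect of interest as the one at the primary time point had patients stayed on treatment, apart from listed events. For hypothetical-strategy stops, SAP 6.3 says that "the patient will still be considered as on-treatment (hypothetically) from an analysis perspective by the statistical models, and during any imputations". Putting the last on-treatment score in the Week 26 slot assumes instead that the score would not have changed after stopping.

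**Working it through.** **1. Is an eEoT test eligible?** An on-time test falls within 7 days of the last dose, and 7 < 12, so it is on-treatment whatever the reason for stopping. The 28-day practice-effect exclusion in SAP 5.1 is written for MCCB only and does not remove it.

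**2. When does it become the Week 26 value?** Only when no later eligible test exists:
- after a hypothetical-strategy stop, if the patient does not restart and no treatment-policy event takes precedence, because a later off-treatment Visit 11 test is barred from mapping;
- after a treatment-policy stop, if there is no later Tower of London test.

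Example: last dose Day 36, eEoT Day 43, hypothetical-strategy event. The Tower of London score becomes Week 26, which is 183 - 43 = 140 days before the planned day. MCCB, VRFCAT or SCoRS done the same day maps to Week 12, and the MMRM treats Week 26 as missing.

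**3. The plan's own figures.** A two-sample t-test with 220 per arm, effect 0.35 and one-sided 0.025 has power 95.6% (stated 95%). The inflation is 440/0.75 = 586.7 (stated 586). A simulation of the gatekeeping procedure (1,000,000 runs) gives Tower of London power of 75.5% in Scenario #1 (stated 75.2%). The planning figures reproduce.

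**4. Upper bound on the share of early values.** Inputs from Protocol 7.5: 293 randomised and 220 evaluable per arm, early termination d = 0.30 to 0.40. Assumption: all completers are evaluable. Early terminators among the 220 are then 220 - 293(1 - d), and the share is s = that number/220. This is an upper bound because it counts every early terminator with a value, including any with a genuine Visit 11 test.

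**5. Dilution.** Ratio of estimate to Week 26 effect = 1 - s(1 - E[f]), where f is the fraction of the Week 26 effect present at the test. Assumption: stopping is uniform over 183 days. E[f] = 0.5 if benefit is linear, and 1 - 84/(2 x 183) = 0.770 if it plateaus at Day 84.

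**6. After a Day 127 start.** A fraction 126/183 = 0.689 of eEoT values drops out. Those that remain have a mean f of (126 + 183)/(2 x 183) = 0.844 (linear) or 1 (plateau).

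| Per arm | d = 0.30 | d = 0.40 |
|---|---|---|
| Completers, 293(1 - d) | 205.1 | 175.8 |
| Early terminators in the 220 | 14.9 | 44.2 |
| Share s | 6.8% | 20.1% |
| Ratio now, linear | 0.966 | 0.900 |
| Ratio now, plateau | 0.984 | 0.954 |
| Values removed, 0.689 x row 2 | 10.3 (4.7%) | 30.4 (13.8%) |
| Analysed after change | 209.7 | 189.6 |
| eEoT values remaining | 4.6 (2.2%) | 13.8 (7.3%) |
| Ratio after, linear | 0.997 | 0.989 |
| Power at 0.275, linear | 79.4 to 80.0% | 73.5 to 75.2% |
| Power at 0.275, plateau | 80.9 to 80.2% | 78.4 to 76.1% |
| Power at 0.2, linear | 52.5 to 53.0% | 46.9 to 48.4% |
| Power at 0.2, plateau | 54.0 to 53.3% | 51.5 to 49.3% |

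Power is stand-alone, two-sample t, one-sided 0.025. Protocol Table 7.5: 1 uses 0.275 in Scenario #1 and 0.2 in Scenarios #2 to #5.

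**7. Stopping pattern.** The documents do not give one. At s = 20.1%, a linearly falling stopping density (E[f] 0.333 linear, 0.611 plateau) gives 1 - 0.201 x 0.667 = 0.866 and 1 - 0.201 x 0.389 = 0.922. A linearly rising density (0.667, 0.930) gives 0.933 and 0.986.

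**The case against.** **It looks like a convention.** Every scale with one post-baseline analysis visit starts at Day 2: Tower of London, SDS, caregiver EQ-5D-5L, SPGI-S, SCQ and the ophthalmological variables. The other tested endpoints can start at Day 127 because an earlier visit absorbs earlier values. This explains the table cell, but Tower of London is the only alpha-controlled endpoint among these scales, and the convention does not turn a Day 43 score into a Week 26 score.

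**On-policy data are relevant.** Protocol Section 7 counts measurements taken while the patient follows the treatment policy as relevant to the primary estimand, and SAP 6.3 excludes only off-treatment data. This stands as far as inclusion goes: using the eEoT score breaks no data-inclusion rule. It does not settle the time point.

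**Tower of London may often be skipped at eEoT.** It is scheduled there, but it is not in the minimum set encouraged in Protocol 6.2.5.1, nor in follow-up Option 2 of Table 6.2.5.1: 1. This stands and could make the share smaller than computed.

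**Redaction.** Parts of the SAP are not visible, and a rationale or sensitivity analysis may exist there. The point concerns the visible main rule.

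**Stronger readings a reader might infer.** One is that a third of analysed values are early. That needs 40% termination with 75% of terminators contributing only an eEoT test: 0.30/0.90 = 33%, with 293 x 0.90 = 264 analysed per arm, well above the plan's 220. Even 50% gives 0.20/0.80 = 25% and 234 per arm. Another is inflated Type I error, which does not follow if the drug affects neither scores nor stopping. A third is that the primary or key secondary results are at risk, but their windows are different.

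**Conclusion.** The mismatch is real on the visible text: for some early stoppers, H4 uses an eEoT score as the Week 26 score. Severity is minor to moderate. H4 sits in Family 3 and is tested only if MCCB and at least one key secondary endpoint succeed. H5 is touched only through the Hochberg step.

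The size is uncertain. At most about 7-20% of analysed values come from early terminators, and the estimate is about 90-97% (linear) or 95-98% (plateau at 12 weeks) of the Week 26 effect. These figures rest on 220 evaluable per arm applying to Tower of London, all completers being evaluable, and uniform stopping. Early-weighted stopping would lower the bottom of the linear range to about 87%. Confidence is high in the mapping and low in the magnitude. The main issue is what the labelled Week 26 estimate means, because power barely moves.

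**What to change.** Before unblinding:
1. In SAP Table 6.7: 3, start the Tower of London Week 26 window at Day 127, the bound the SAP already uses for the other four tested endpoints.
2. Leave earlier values missing at Week 26 in the planned ANCOVA, consistent with the default in SAP 6.6 that missing data are not imputed.
3. Report the current Day 2 rule as a sensitivity analysis.

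Multiple imputation following the split in Protocol 7.2.2 (off-treatment donors after treatment-policy events, on-treatment donors otherwise, same arm) may be added as a further sensitivity analysis. It should not become the main analysis. Off-treatment donors may be few, and at the plan's assumed correlation of 0.2 between endpoints, Week 12 MCCB explains only 0.2 squared = 4% of the variance.

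Cost: one table cell and a short paragraph. Analysed values fall by about 5-14% (from 220 to about 210-190 per arm). Power changes by about +1 to +2 points if benefit is linear and by about -1 to -2 if it plateaus. Day 127 is not validated for this scale, and some eEoT values from Day 127 on would remain. Dropping earlier values also relies on missingness being explained by treatment, stratum and baseline, which is a reason to keep the sensitivity analyses.
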